## 3 Trial Objectives and Endpoints

### 3.1 Objectives

#### Primary Objective

- To evaluate the effect of individualised FE 999049 treatment on ovarian response in a long GnRH agonist protocol versus a GnRH antagonist protocol

#### Secondary Objectives

- To evaluate the effect of individualised FE 999049 treatment on other pharmacodynamic parameters in a long GnRH agonist protocol versus a GnRH antagonist protocol
- To evaluate the effect of individualised FE 999049 treatment on pregnancy rates in a long GnRH agonist protocol versus a GnRH antagonist protocol
- To evaluate the safety of individualised FE 999049 treatment in a long GnRH agonist protocol versus a GnRH antagonist protocol

### 3.2 Endpoints

#### Primary Endpoint

- Number of oocytes retrieved

#### Secondary Endpoints

- Proportion of subjects with cycle cancellation due to poor ovarian response or excessive ovarian response
- Proportion of subjects with blastocyst transfer cancellation after oocyte retrieval due to (risk of) OHSS
- Number and size of follicles on stimulation day 6 and end-of-stimulation
- Proportion of subjects with <4, 4-7, 8-14, 15-19 and ≥20 oocytes retrieved
- Number of metaphase II oocytes (only applicable for subjects where all oocytes are inseminated using ICSI) fertilisation rate as well as number and quality of embryos on day 3 and blastocysts on day 5 after oocyte retrieval

- Circulating concentrations of FSH, luteinising hormone (LH), estradiol, progesterone and inhibin B on stimulation day 6, end-of-stimulation and at oocyte retrieval
- Total gonadotropin dose and number of stimulation days
- Positive  $\beta$ hCG rate (positive serum  $\beta$ hCG test 13-15 days after transfer)
- Implantation rate (number of gestational sacs 5-6 weeks after transfer divided by number of blastocysts transferred)
- Clinical pregnancy rate (at least one gestational sac 5-6 weeks after transfer)
- Vital pregnancy rate (at least one intrauterine gestational sac with fetal heart beat 5-6 weeks after transfer)
- Ongoing pregnancy rate (at least one intrauterine viable fetus 10-11 weeks after transfer)
- Ongoing implantation rate (number of intrauterine viable fetuses 10-11 weeks after transfer divided by number of blastocysts transferred)
- Proportion of subjects with early OHSS (including OHSS of moderate/severe grade)
- Proportion of subjects with late OHSS (including OHSS of moderate/severe grade)
- Frequency and intensity of adverse events
- Technical malfunctions of the pre-filled injection pen

### 3.3 Post-trial Information

- Live birth rate and neonatal health, including minor/major congenital anomalies, at birth and at 4 weeks after birth

#### 4 Trial design

This is a randomised, controlled, open label, parallel group, multicentre trial comparing the efficacy and safety of individualised FE 999049 dosing in first cycle patients aged 18-40 years undergoing controlled ovarian stimulation for IVF/ICSI following either a long GnRH agonist protocol or a GnRH antagonist protocol. The trial has been designed to describe potential differences in the mean number of oocytes retrieved with adequate precision.

Subjects will be screened within 90 days prior to randomisation for compliance with the inclusion and exclusion criteria. Randomisation may take place as soon as all eligibility criteria are met. Subjects will be randomised in a 1:1 ratio to controlled ovarian stimulation with FE 999049 in a long GnRH agonist protocol or to controlled ovarian stimulation with FE 999049 in a GnRH antagonist protocol. Randomisation will be stratified by centre and according to age (<35, 35-37 and 38-40 years). The subject will be informed of treatment allocation and when to start treatment by the delegated trial staff.

Subjects randomised to treatment with FE 999049 in the long GnRH agonist protocol will start down-regulation with GnRH agonist (triptorelin acetate, GONAPEPTYL) 0.1 mg/day subcutaneously in the mid-luteal phase (i.e. cycle day 21-24) of their menstrual cycle. Ovarian stimulation with FE 999049 will start after 14 days ( $\pm 1$  day) if the subject has experienced withdrawal bleeding and down-regulation criteria are fulfilled. If down-regulation is confirmed and ovarian stimulation is initiated, treatment with GnRH agonist is continued throughout the stimulation period. If the subject has not experienced withdrawal bleeding after 14 days ( $\pm 1$  day), a urinary pregnancy test is to be performed. If the subject is not pregnant and down-regulation is not confirmed, treatment with GnRH agonist will be continued and stimulation will be postponed until down-regulation is confirmed. Subsequent visit(s) for confirmation of down-regulation will be scheduled according to local practice. If down-regulation is not achieved after 28 days, treatment with GnRH agonist will be stopped and the subject will be withdrawn from the trial.

Subjects randomised to treatment with FE 999049 in the GnRH antagonist protocol will start stimulation with FE 999049 on day 2 or 3 of their menstrual cycle. To prevent a premature LH surge, a GnRH antagonist (cetrorelix acetate, CETROTIDE) 0.25 mg/day subcutaneously will be initiated on stimulation day 6 and continued throughout the stimulation period.

Subjects will have their individual FE 999049 dose determined on the basis of their AMH level at screening and their body weight on stimulation day 1. The daily FE 999049 dose will be fixed throughout the stimulation period. For subjects with AMH  $<15$  pmol/L the daily FE 999049 dose is 12  $\mu$ g, irrespective of body weight. For subjects with AMH  $\geq 15$  pmol/L the daily FE 999049 dose is on a continuous scale ranging from 0.19 to 0.10  $\mu$ g/kg, i.e. dependent on actual AMH and body weight. AMH will be measured by Elecsys® AMH Plus Immunoassay (Roche Diagnostics). The maximum allowed daily FE 999049 dose is 12  $\mu$ g. Subjects can be treated with FE 999049 for a maximum of 20 days, and coasting is not allowed.

During stimulation, subjects will be monitored by transvaginal ultrasound on stimulation day 1 and 6 and hereafter at least every second day. When the leading follicle reaches  $\geq 15$  mm, visits must be performed daily. Triggering of final follicular maturation will be done as soon as  $\geq 3$  follicles with a diameter  $\geq 17$  mm are observed. If there are  $< 25$  follicles with a diameter  $\geq 12$  mm, a single dose of hCG (OVITRELLE) 250  $\mu$ g will be administered. If there are  $\geq 25$  follicles with a diameter  $\geq 12$  mm, the cycle will be cancelled. If it is judged by the investigator that  $\geq 3$  follicles with a diameter  $\geq 17$  mm cannot be reached, but 1 or 2 follicles with a diameter  $\geq 17$  mm are observed, the cycle may either be cancelled due to poor follicular development or triggering of final follicular maturation is to be induced, as judged by the investigator.

Oocyte retrieval will take place 36h ( $\pm 2$ h) after triggering of final follicular maturation and the oocytes can be inseminated by IVF and/or ICSI. Fertilisation and embryo development will be assessed from oocyte retrieval to the day of transfer. For all subjects blastocyst transfer is performed on day 5 after oocyte retrieval. Subjects  $< 38$  years at randomisation will have single blastocyst transfer. Subjects  $\geq 38$  years at randomisation will have single blastocyst transfer if they have a good-quality blastocyst available, i.e. a blastocyst of grade 3BB or higher; otherwise they may have double blastocyst transfer. Remaining blastocysts may be cryopreserved and used by the subject after completion of the trial, in accordance with local guidelines and/or regulations. All procedures and assessments related to cryopreserved cycles will take place outside this protocol and will not be paid for by Ferring.

Vaginal progesterone tablets (LUTINUS) 100 mg three times daily will be provided for luteal phase support from the day after oocyte retrieval and until the serum  $\beta$ hCG test. Luteal phase support may be continued after a positive  $\beta$ hCG is obtained if this is local practice. A serum  $\beta$ hCG test is performed 13-15 days after transfer, clinical pregnancy will be confirmed by transvaginal ultrasound 5-6 weeks after transfer, and ongoing pregnancy will be confirmed by transvaginal or abdominal ultrasound 10-11 weeks after transfer.

Blood samples will be collected throughout the trial for the purpose of evaluating the endocrine profile assessed at screening, stimulation day 1, stimulation day 6, end-of-stimulation and at oocyte retrieval.

## Post-trial Activities

Post-trial activities cover pregnancy and neonatal health follow-up. All subjects with an ongoing pregnancy will be followed till delivery to gather information on live birth rate. Furthermore, data will be gathered on neonatal health, including minor/major congenital anomalies, at birth and at 4 weeks after birth. These data will be reported separately.

### 4.1 Design Considerations

The trial will be open label as a double-blind design is not feasible due to the required GnRH agonist treatment prior to start of stimulation in a long GnRH agonist protocol. In contrast, in a GnRH antagonist protocol, the GnRH antagonist is only started during the mid-follicular phase of

the stimulation period. Prior to start of stimulation in a long GnRH agonist protocol, down-regulation needs to be confirmed based on ultrasound findings, thus neither patients nor the assessors in this trial can be blinded. The lack of blinding may result in different withdrawal patterns for the two protocols. To minimise this, only subjects without strong preference for one of the protocols will be included. No measures are taken to prevent investigators, delegated trial staff or subjects from knowing the treatment allocation.

Subjects with an AMH level  $>35$  pmol/L at screening will be excluded from the trial as these subjects are likely to have polycystic ovaries and may have an increased risk of OHSS.

The primary endpoint of this trial will allow the comparison of distribution of the number of oocytes retrieved following each GnRH analogue protocol, and more specifically in subjects with low AMH ( $<15$  pmol/L) and high AMH ( $\geq 15$  pmol/L). Based on current knowledge about the difference in ovarian response following treatment with CHO-derived rFSH in either protocol an overall treatment difference of at least 1 oocyte is to be anticipated, the difference being smaller in subjects with low AMH than in subjects with high AMH. This treatment difference, especially in subjects with high AMH, will indicate whether the FE 999049 dosing algorithm remains safe and effective when applied in a GnRH agonist protocol.

#### **4.2 Determination of Sample Size**

The purpose of this trial is to gain clinical experience with the use of FE 999049 when applied in a long GnRH agonist protocol. The trial is descriptive and does not include any hypothesis testing. The sample size is based on achieving a reasonable precision in the estimate of the difference in mean number of oocytes retrieved between treatment with FE 999049 in a long GnRH agonist protocol versus treatment with FE999049 in a GnRH antagonist protocol.

In the ESTHER-1 trial, the standard deviation for the number of oocytes retrieved was 5.8 in the FE 999049 treatment group. Due to a potentially higher number of oocytes retrieved in the long agonist protocol, the standard deviation in this trial may be slightly higher. Assuming a standard deviation of 7.0, a sample size of 400 subjects (200 subjects per group) will give a 95% CI that ranges from -1.4 to +1.4 of the observed mean difference, i.e. the interval from the observed mean difference -1.4 to the observed mean difference +1.4 will with 95% probability include the true mean difference. This is regarded to be reasonably precise for describing the comparability of individualised FE 999049 dosing using the two protocols.

## 5 Subject Disposition

All subjects screened and randomised will be accounted for. All post-randomisation discontinuations will be summarised by time of, and reason for, discontinuation. Discontinuations will be classified as occurring before or after start of FE 999049 treatment. The number of subjects screened and not randomised will be presented.

## 6 Protocol Deviations

Important protocol deviations will be summarised and listed by subject. The impact of important protocol deviations on the trial results may be addressed in additional sensitivity analyses.

## 7 Analysis sets

### 7.1 Full Analysis Set

The FAS will consist of all subjects that were randomised, regardless of whether they started FE 999049 treatment or not. However, subjects that discontinued before starting FE 999049 treatment due to the COVID-19 pandemic (e.g. due to operational and/or societal issues) will be excluded from the FAS. In the analyses of efficacy endpoints subjects will be analysed according to the protocol to which they were randomised.

### 7.2 Safety Analysis Set

The safety analysis set will consist of all subjects that were randomised in the trial and were exposed to FE 999049. In all presentation of safety data subjects will be presented according to the protocol they were actually treated with.

## 8 Trial population

### 8.1 Demographics and Other Baseline Characteristics

Descriptive statistics of demographics and other baseline characteristics (body measurements, infertility history, menstrual history, reproductive history, smoking and alcohol habits, physical examination, and gynaecological examination) will be presented for the FAS. In addition, a summary of demographic characteristics will be presented by trial site.

### 8.2 Medical History and Concomitant Medication

Medical history and concomitant medication will be presented for the FAS. Medical history recorded at the screening visit will be coded using MedDRA and summarised. The version of MedDRA will be documented. Prior and concomitant medication will be summarised by ATC classification 1st level (alphabetically) and ATC classification 2nd level (in decreasing order of frequency). These medications will be tabulated separately for:

- Prior medication, i.e. medication taken exclusively prior to treatment (i.e. with stop date/time before date/time of 1st IMP administration)

- Concomitant medication, i.e. medication taken during the treatment period (i.e. medication that was not stopped before date/time of 1st IMP administration and not started after the end-of-trial visit)

If the timing of the dose of a concomitant medication cannot be established in relation to the administration of IMP, it will be considered as concomitant medication.

## **9 Treatment Compliance**

Number of days with GnRH agonist and GnRH antagonist treatment will be summarised.

Compliance with progesterone treatment for luteal phase support will be summarised (number of days with treatment, completed according to instruction, number of tablets missed, and prematurely stopped due to menstrual bleeding).

## 10 Efficacy

### 10.1 General Considerations

The primary objective of the trial is to evaluate the effect of individualised FE 999049 treatment on ovarian response in a long GnRH agonist protocol versus a GnRH antagonist protocol. The primary endpoint is the number of oocytes retrieved.

The estimand of interest is the difference between FE 999049 treatment in the long GnRH agonist protocol versus treatment with FE 999049 in the GnRH antagonist protocol for all randomised subjects, assuming that all subjects start treatment with FE 999049. In the statistical analyses, subjects that discontinue after randomisation but before start of FE 999049 treatment (except for subjects that never started treatment due to the COVID-19 pandemic, which are not included in any analysis) will have their endpoint data imputed from subjects who started FE 999049 treatment in the same protocol, using a multiple imputation method. No imputation will be done for subjects who discontinue the trial after starting FE 999049 treatment. For these subjects, the actual data will be used and not be regarded as missing. Therefore, the number of oocytes retrieved will be regarded as zero and pregnancy outcomes will be regarded as negative.

The trial is descriptive and no formal hypothesis will be tested. The statistical analyses aims at estimating any potential differences between FE 999049 treatment when applied in the two different GnRH protocols. The results will generally be described as an estimated mean treatment difference or treatment ratio and an associated 95% confidence interval.

Since the trial is descriptive without any hypothesis testing, no corrections for multiplicity will be applied.

Analyses and descriptions for ovarian response endpoints and other pharmacodynamics endpoints will be based on the FAS. Analyses and descriptions for pregnancy endpoints will be based on the FAS but excluding subjects that had transfer cancellation due to the COVID-19 pandemic.

Additional descriptions for pregnancy endpoints will be made based on the FAS (i.e. including also the subjects with transfer cancellation due to the COVID-19 pandemic). Analyses and descriptions of safety endpoints and exposure will be based on the safety analysis set.

Subjects in the FAS that did not start treatment with FE 999049 will not have any data after exposure to FE 999049. For these subjects, post-randomisation data will only be imputed for the purpose of statistical analysis, using multiple imputation techniques. In tables, figures and listings all post-randomisation data from these subjects will be missing. Therefore tables, figures and listings will be based on subjects in the FAS starting treatment with FE 999049, i.e. randomised and exposed subjects (i.e. same as the safety analysis set).

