$$m_{MI} = \frac{1}{1000} \sum_{i=1}^{1000} m_i, \quad SD_{MI} = \sqrt{\frac{1}{1000} \sum_{i=1}^{1000} SD_i^2 + \left(1 + \frac{1}{1000}\right) \left(\frac{1}{1000 - 1}\right) \sum_{i=1}^{1000} (m_i - m_{MI})^2}$$

Where  $m_i$  and  $SD_i$  are the estimated mean differences and standard deviations for the differences for the 1000 copies of the dataset (derived using the delta method), and  $m_{MI}$  and  $SD_{MI}$  are the pooled estimates.

- The mean difference in number of oocytes retrieved between the long GnRH agonist protocol and the GnRH antagonist protocol will be estimated as  $m_{MI}$ , and the 95% CI for the estimate will be calculated as  $m_{MI} \pm 1.96 * SD_{MI}$ .

The assumption underlying the above imputation procedure is that all randomised subjects could have started FE 999049 treatment, and that their outcome would not have differed in any systematic way from the subjects that started FE 999049 treatment.

For subjects who discontinue the trial after start of FE 999049 treatment but before oocyte retrieval the number of oocytes retrieved will be regarded as zero.

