## **Pregnancy Rates**

The percentage of subjects with positive  $\beta$ hCG, clinical pregnancy, vital pregnancy, and ongoing pregnancy will be described for each of the two protocols and for subgroups based on age strata and AMH. Pregnancy rates will be compared between the long GnRH agonist protocol and the GnRH antagonist protocol using a logistic regression model with treatment (long GnRH agonist or GnRH antagonist), age stratum ( $<35$ , 35-37, or 38-40 years), and AMH at screening ( $<15$  pmol/L or  $\geq 15$  pmol/L) as factors. The results of this analysis (in terms of odds for pregnancy) will be converted into proportions, differences in proportions, and 95% CIs for differences in proportions using the delta method.

To account for subjects withdrawing from the trial before starting FE 999049 treatment, the multiple imputation method applied for the primary endpoint will be used, using a logistic regression model instead of a negative binomial regression model. Pregnancy data for subjects with pregnancies occurring before start of FE 999049 treatment will not be included in the analysis. These subjects are withdrawn and their data will be imputed.

Missing pregnancy assessments will be assumed to indicate a negative test. If, however, a subsequent test is positive, a previous missing assessment will be considered as positive (if e.g. the clinical pregnancy assessment is missing but the ongoing pregnancy assessment is positive, the missing clinical pregnancy assessment will be regarded as positive).

The main analyses of pregnancy rates will be based on subjects in the FAS, but excluding subjects that had transfer cancellation due to the COVID-19 pandemic. Additional analyses will be made for the FAS, and also for subjects in the FAS that started treatment with FE 999049, i.e. without using multiple imputations (i.e. the safety analysis set).

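### A COVID-19 stop between first FE 999049 dose and oocyte retrieval is scored as zero oocytes and not pregnant, unlike COVID-19 stops before first dose or at transfer

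*SAP*

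**What the plan says.** The plan handles COVID-19 in two windows and is silent in the one between them.

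- **Before first dose.** SAP 7.1 (and protocol 9.4.1): those who "discontinued before starting FE 999049 treatment due to the COVID-19 pandemic (e.g. due to operational and/or societal issues) will be excluded from the FAS".
- **First dose to oocyte retrieval.** SAP 10.1 states that "No imputation will be done for subjects who discontinue the trial after starting FE 999049 treatment" and continues: "Therefore, the number of oocytes retrieved will be regarded as zero and pregnancy outcomes will be regarded as negative". SAP 10.2 gives the window for the primary endpoint: for stops "after start of FE 999049 treatment but before oocyte retrieval the number of oocytes retrieved will be regarded as zero". Protocol 9.6.1 and 9.6.2 carry the same rule. None of these sections makes an exception for COVID-19.
- **At transfer.** SAP 10.1 bases the pregnancy analyses on the "FAS but excluding subjects that had transfer cancellation due to the COVID-19 pandemic", and SAP 10.3 adds further analyses on the whole FAS. These women keep their real oocyte counts in the primary analysis.

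Under protocol 7.2.4 a zero falls in the <4 class, which is labelled low response.

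**The concern.** The primary objective is ovarian response. Zero is a fair score when poor or excessive response ended the cycle. It says nothing about response when a woman with a normal follicle cohort stops because her clinic closed or she had to isolate.

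The same cause is handled in opposite ways depending on the day it strikes. The comparison with transfer is the telling one: a woman whose transfer is cancelled because of the pandemic has also been dosed, yet she leaves the main pregnancy analysis. A woman stopped during stimulation stays in it as not pregnant.

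The artificial zeros reach the primary endpoint, the <4 class, the pregnancy rates, and the fertilised-oocyte, embryo and blastocyst counts analysed by the primary method. They also enter the imputation model, because SAP 10.2 fits it to everyone who started treatment; values imputed for never-starters are then drawn from a distribution containing these zeros.

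Nothing else in the plan corrects this. The supplementary analysis of treated women in SAP 10.2 keeps the zeros. The sensitivity analyses for protocol deviations in SAP 6 are optional and do not name COVID-19. The disposition tables in SAP 5 show reasons for stopping but change no estimate.

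**Working it through.** **Inputs.** SD 7.0, 200 women per arm and half-width 1.4 (SAP 4.2). Anticipated difference at least 1 oocyte (SAP 4.1). From ESTHER-1, FE 999049 arm (protocol 1.1): mean 9.6 oocytes for all randomised, 11.2 for AMH ≥15 pmol/L, ongoing pregnancy 30.7%. The number of COVID-19 stops in the window, k, is not in the documents; 1 to 10 per arm is an assumption.

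**1. The plan's precision.** Half-width = 1.96 × 7.0 × √(1/200 + 1/200) = 1.96 × 7.0 × 0.1 = 1.372, stated as 1.4. It reproduces.

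**2. Effect of k such stops.** If they fall in one arm only, the difference shifts by 9.6 × k/200. If they fall equally in both arms, a true difference of 1.0 shrinks to 1.0 × (1 − k/200). The expected fall in an affected arm's ongoing pregnancy rate is 30.7 × k/200 percentage points, because only about 31 in 100 such women would otherwise have had an ongoing pregnancy.

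| k | Shift, one arm only (oocytes) | Share of 1.372 | True 1.0, k in both arms | Fall in ongoing pregnancy (points) |
|---|---|---|---|---|
| 1 | 0.048 | 3.5% | 0.995 | 0.15 |
| 2 | 0.096 | 7.0% | 0.990 | 0.31 |
| 5 | 0.24 | 17.5% | 0.975 | 0.77 |
| 10 | 0.48 | 35% | 0.950 | 1.53 |

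To move the difference by a whole oocyte would take 1.0/9.6 × 200 = 20.8, or about 21 excess stops in one arm.

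**3. The <4 class.** Each woman adds at most 1/200 = 0.5 points, and less in expectation because some would have had fewer than 4 oocytes anyway.

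**4. High-AMH subgroup.** SAP 4.1 relies on this difference to judge the dosing algorithm. Its size is not given. If 80, 100 or 120 of an arm's 200 women have AMH ≥15 pmol/L (assumption), one zero there lowers the subgroup arm mean by 11.2/80 = 0.14, 11.2/100 = 0.11 or 11.2/120 = 0.09 oocyte.

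**5. Precision lost by not scoring them.** Dropping k women per arm gives 1.96 × 7.0 × √(2/(200 − k)): 1.375 for k = 1, 1.389 for k = 5 and 1.408 for k = 10. The loss is negligible.

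**The case against.** The best defence is that this is a choice of estimand. The hypothetical part extends only to assuming that everyone starts FE 999049; from then on, what happened counts. The rule is explicit, covers every reason for stopping, and sits in the same text that deals with COVID-19. This does not fully stand, because the transfer rule removes women who have already been dosed, so the plan does not hold to that principle.

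Transfer cancellation could also be read broadly enough to include a stop during stimulation. The documents point the other way: the endpoint list separates cycle cancellation from transfer cancellation after retrieval, and protocol 7.2.2 ties the OHSS version to women with blastocysts available. A broad reading would in any case repair only the pregnancy analyses.

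Three objections stand in whole or part:

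- **Attribution.** In this window unblinded staff can see follicle counts, so a COVID-19 label could be influenced by a visibly poor response. This is a reason to show both results. It is not a reason to keep only the zero-scored one, since unblinded attribution is already accepted in the other two windows.
- **Balance.** Randomisation is 1:1 in blocks within centre (protocol 4.2.2), so a closure tends to strike both arms. Stimulation lasts at most 20 days, with about one more day expected under the agonist protocol. A large imbalance is unlikely.
- **Effort.** The rule is in the protocol too, so more than a clarification of the SAP is needed.

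**Conclusion.** The gap is real and should be closed before database lock. Its size is probably modest: about 0.05 oocyte and 0.15 points of ongoing pregnancy per woman, and 0.24 oocyte for an assumed excess of 5 in one arm. One or two cases would not change the reading of a descriptive trial. These figures assume ESTHER-1 means and rates, 200 women per arm, and that the affected women would have responded like the rest of their arm.

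A reader might infer more than the documents support:

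- *Every stop after first dose is affected.* The zero applies only before retrieval; afterwards the actual count is used.
- *These women are counted as poor responders throughout.* The endpoint on cycle cancellation for poor or excessive response uses the recorded reason (protocol 7.2.1) and is not affected.
- *Each woman costs half a point of pregnancy rate.* One in 200 is 0.5 points, but most such women would not have had an ongoing pregnancy anyway; the expected loss is 0.307/200, about 0.15 points.
- *The arm difference will be biased.* That needs unequal numbers by arm, for which the documents give no evidence. Equal numbers only shrink the difference slightly.

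**What to change.** 1. Before database lock, and without reference to oocyte or follicle data, list the women whose recorded reason for stopping between first dose and retrieval is COVID-19. Report their number by arm.
2. SAP 10.3: exclude them from the main pregnancy analyses, as for COVID-19 transfer cancellations, and keep the FAS result alongside.
3. SAP 10.1 to 10.3: treat their oocyte count, and the counts and classes derived from it, as missing. Impute with the existing model for each protocol, fitted without these women, and report the zero-scored result alongside. At minimum, pre-specify the COVID-19-as-missing analysis as a named sensitivity analysis of the primary endpoint.
4. Record the change in SAP 14 as a departure from protocol 9.6.1 and 9.6.2, and amend the statement in SAP 2 that no analyses change.

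The cost is low. Reasons for discontinuation are already collected (protocol 4.4 and 7.3.16) and the imputation method exists, needing only a changed fitting set. The remaining weakness is that unblinded staff who can see follicle counts make the attribution, which is why both results are shown.
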